We produced a kind of new solution for submucosal injection, named EndoGel, a Class II medical device. This clinical trial aims at recruiting patients who are diagnosed with polypoid lesions in their esophagus, stomach or intestines. In these patients endoscopic dissection or endoscopic mucosal resection is considered the most appropriate treatment for them. In our clinical trial, we intend to inject EndoGel in the submucosal area of the targeted lesion in patients' esophagus, stomach or intestines to facilitate the performance of ESD. The purpose of this clinical trial is to

evaluate the safety and efficacy of using EndoGel in ESD and endoscopic dissection of superficial tumors.

I. Introduction

1.1 Background

The westernization of Asian diets has increased the incidence of polyps and early cancers of gastrointestinal tract in Taiwanese people. Accordingly, there is a sharp surge in the number of people who undergo regular health screenings. Also, the number of patients doing esophago-gastro-duodenoscopy (EGD), polypectomy resection and endoscopic submucosal dissection (ESD) increases remarkably. As evidences show that effective polypectomy in GI tract can prevent future cancer evolving from the previous polyps, the device to facilitate the preemptive technology is important, we invent our EndoGel for this purpose.

Normal saline is widely used as the solution for submucosal injection in endoscopic treatment. However, the fluid appears lost in the mists of time, and only maintains the submucosal cushion for a short period of time. The drawbacks make endoscopic surgeries more difficult, increasing the risks of harming deep mucosal tears while dissections. On the other hand, the loss of normal saline causes repeated injections and thus prolongs the time of endoscopic dissection. To overcome the current limitations, more ideal solutions for submucosal injection are developed. Hyaluronic acid is now the most optimal solution for submucosal injection, but it is not covered by Health Insurance and thus very expensive. As a result, it is not widely used by most countries around the world.

In the United States, methylcellulose being the primary material, a new solution for submucosal injections is invented. This solution is now approved to be a Class II medical device by FDA. But it is neither registered nor clinically-used in Taiwan due to its high cost and weak promotion. In the past, most doctors in Taiwan used normal saline with higher concentration (3%) or glucose solutions (20%, 30%, 50%) for submucosal injection. These solutions are easy to access and comparatively cheaper;

moreover, they remain in the submucosal area longer than normal saline does. However, inflammatory reactions usually occur at the spots where physicians inject these solutions. Consequently, most Taiwanese endoscopists now use Glycerol (10%) or Hyaluronic acid at patients' own expense as the solution for submucosal injection. But another problem rises; TFDA did not officially permit physicians to use these solutions in endoscopic surgeries. In other words, the cost of them is a grey area.

By contrast, our medical device, EndoGel, is composed of calcium lactate and sodium alginate, both of which have been widely used clinically in Taiwan. TFDA has approved the use of 0.3% alginate in 500ml for intravenous injection. As a result, sodium alginate is considered safe and applicable. Further, the Handbook of pharmaceutical excipient explicitly lists it as a GRAS substance, with LD50 (cat, IP): 0.25g/kg, LD50 (rabbit, IV): 0.1g/kg and LD50 (rat, IP): 0.25g/kg. Expectedly, we assume that the locally injected volume of alginate is below 50ml in single administration. If the patient is of 50 kg, the optimal dose of alginate for him/her is 0.01g/kg. Furthermore, alginate leaks from the wound after therapy.

Calcium lactate has also been used commonly in Taiwan for many years. It is used in the treatment of Hypocalcemia, Osteoporosis and Postmenopausal, and can be intravenously injected. Calcium lactate is also regarded as GRAS. Expectedly, we assume that the locally injected volume of alginate is below 50ml in single administration. If the patient is of 50 kg, the optimal dose of calcium lactate for him/her is 0.02g/kg.

After we mix sodium alginate and calcium lactate, the viscosity of the mixed solution increases due to cross-linking. Thus, the solution can create an optimal height of submucosal cushion with its high viscosity. The results of pre-clinical trials also manifested that the effect of this solution in submucosal elevation is equivalently good as that of Hyaluronic acid, and even better than that of Glycerol! Animal body ESD also showed the feasibility of this solution in submucosal elevation.

Consequently, we formally submitted an application for using this solution, named EndoGel, in submucosal injection; we also requested for the consent of TFDA

to conduct clinical trials for a class II medical device to investigate EndoGel. Besides, because *EndoGel* has been registered, we would change the name of the intervention as *AceGel* to prevent misunderstanding and other problems in the future.

1.2 Clinical Trial Guidance

This clinical trial is performed in accordance with *Clinical Investigation of Medical Devices for Human Subjects-Good Clinical Practice* (ISO 14155-1, -2). Before we recruited the patients, we had sent all the documents such as proposals and clinical trial informed consents to IRB of National Cheng Kung University and TFDA, and consequently they have approved this case. Afterwards, we started to recruit patients with all the procedures in conformance with what has instructed in *Clinical Investigation of Medical Devices for Human Subjects-Good Clinical Practice*.

During the recruitment process, IRB at National Cheng Kung University audited the relevant documents on August 31st, 2018, and provided us with instructions and suggestions.

II. Materials and Methods

2.1 Description of Medical Devices

EndoGel is a solution for submucosal injection. It can be used to lift gastric lesions when being injected into the submucosal areas during ESD or EMR. The submucosal cushions help endoscopists efficiently remove the lesions with electric probes or polypectomy snares, offering patients a less invasive option for gastrointestinal cancer treatment.

EndoGel is composed of calcium lactate and sodium alginate, both of which are considered “Generally recognized as safe” (GRAS). After mixing the two substances, the viscosity of the solution increases due to cross-linking. Hence, the solution can

serve as the submucosal injective solution used for treatments of early gastrointestinal cancer, and can effectively prevent surgical complications such as bleeding and perforation. Ideally, the suggested mixing ratio is 1:1, but ratios ranging from 0.5:1 to 2:1 can still successfully trigger gelation of the mixed solution. Besides, we dye calcium lactate blue to help endoscopists to mark the lesions to be removed. As a result, we suggest that the injection of Calcium lactate (the blue one) precedes the injection of Sodium alginate (the white one) during ESD or EMR. Or alternatively, endoscopists can use a double diameter syringe to inject the two solutions simultaneously to the targeted lesion.

During the trials, the physicians who performed ESD and EMR with EndoGel pointed out a pivotal drawback; they found that due to the repeated injections of EndoGel, the pressure in syringes was so high that the duration of surgery was extended. To overcome this problem, we adjusted the concentration and ratio of the components in EndoGel to create the desired proportion which meets the physicians' need. The adjustment is shown in the following table;

EndoGel After Adjustment	
Component	Volume
Sodium alginate	100mg
Calcium lactate	400mg
EndoGel is a product used for endoscopic therapy. We suggest that physicians inject calcium lactate (the vial with blue powder) first and sodium alginate (the vial with white powder) later.	
How to dilute sodium alginate: First, infuse the sodium alginate powder with 10-20mL sterile water or normal saline. Second, shake the vial for 30 to 60 seconds until the solution is clear without floating particles on the surface. Afterwards, draw the solution to fill a 3mL syringe with a needle. The purpose of using a 3mL syringe is to reduce the resistance while injecting.	

How to dilute calcium lactate:

First, infuse the calcium lactate powder with 10-20mL sterile water or normal saline. Second, shake the vial well and draw the solution out with a 10mL syringe with a needle.

How to use EndoGel:

Fill the endoscopic aspiration syringes with calcium lactate and sodium alginate, and inject them respectively to the submucosal area of targeted lesions. Before injecting the second solution, fill the syringe with sterile water or normal saline to wash the residue solution within it away. If not, the remnant of calcium lactate is likely to become gel which obstructs the syringe when mixing with alginate.

2.2 Abstract of the clinical trial

Endoscopic Submucosal Dissection (ESD) is an endoscopic technique which aims at dissecting mucosal lesions completely. Speaking of ESD, it is of importance to select the appropriate patients and lesions. The standard operation procedure includes the following steps: marking of the lesions, repeated submucosal injections, lesion resections, repeated submucosal dissections and removal of lesions. Making use of various endoscopic devices will facilitate submucosal dissection of lesions swiftly and safely. Furthermore, an ideal mucosal elevation can also help doctors dissect lesions effectively. A suitable solution for submucosal injection can provide a thick submucosal fluid cushion, remain in the submucosal area long enough to securely allow ESD and preserve the tissue specimen which allows for pathological examinations.

Normal saline used to be one of the most widely-used solutions for submucosal injection. However, it can only maintain the submucosal cushion for a short period of time. To overcome the current limitations, more ideal solutions for submucosal injections are developed. Hyaluronic acid is now the most optimal solution for submucosal injection, but it is not covered by Health Insurance and thus very

expensive. As a result, our project aims at developing a better solution for submucosal injection.

Our project produced a kind of new solution for submucosal injection, named EndoGel. We have conducted in vitro and in vivo assays of pigs with EndoGel. The results showed no serious complications occurring to the pigs in vivo.

2.2.1 Goal of the clinical trial

The primary goal of this clinical trial is to evaluate the safety and efficacy of using EndoGel in ESD and endoscopic dissection of superficial tumors clinically.

2.2.2 Design of the clinical trial

2.2.2.1 Experiment design

We aim at recruiting 12 patients who are diagnosed with gastrointestinal superficial tumors to conduct clinical trial therapies.

EndoGel is the solution used for submucosal injection for all candidates. The usage of EndoGel is listed below;

1. Infuse 10-20mL normal saline into the vial with blue powder of calcium lactate. Shake the vial well and then draw the solution out with a 10mL syringe with a needle.
2. Infuse 10-20mL normal saline into the vial with white powder of sodium alginate. Shake the vial well until no floating particles can be seen on the surface. Draw the solution out with a 3 mL syringe with a needle. Mix the two solutions in conformance with the suggested mixing ratios given in **section 2.1**.
3. Fill the endoscopic aspiration syringes with calcium lactate and sodium alginate, and inject them respectively to the submucosa beneath targeted

lesions. Before injecting the second solution, fill the syringe with sterile water or normal saline to wash the residue solution within it away. If not, the remnant of calcium lactate is likely to become gel which obstructs the syringe when mixing with alginate.

4. After mixing the two substances, the viscosity of the solution increases due to cross-linking. EndoGel will create a submucosal cushion with an optimal height. Remove the lesions with electric probes or polypectomy snares by dissecting the elevated cushion.

The administered dose and injection times of EndoGel can be determined based on the size of lesions and the height of submucosal cushions. Physicians will perform the endoscopy surgery in endo rooms or operation rooms after clinical assessment. The standard operation procedure includes the following steps;

Endoscopic submucosal dissection (ESD):

- (1). Mark the perimeter of the lesion with cautery.
- (2). Inject the lifting agent to the submucosa around the perimeter of the lesion. In this trial, the lifting agent is the mixed solution of alginate and calcium lactate.
- (3). Incise the elevated submucosa and circumferentially cut the perimeter of the lesion with an electrosurgical knife.
- (4). Dissect the submucosa beneath the lesion by an electrosurgical knife until the lesion is completely resected.
- (5). Manage any complications such as intraprocedural bleedings and perforations.
- (6). Make sure there is no bleedings or perforations after the dissection of lesions. If so, do the appropriate management. If not, ESD is officially completed.

Endoscopic mucosal resection (EMR):

- (1). Formulate a resection strategy. Make sure the lesions could be successfully removed via snare excision.
- (2). Inject the lifting agent to the submucosa around the lesion. In this trial, the lifting agent is the mixed solution of alginate and calcium lactate.
- (3). Use polypectomy snares to excise the lesions.
- (4). Manage any complications such as intraprocedural bleedings and perforations.

After the therapy, we will monitor the vital signs of the patients in wards or endo rooms. We carry out the medical observation in order to react promptly to any immediate adverse events occurring to the patients, such as delayed bleedings and perforations. We will also conduct long term follow-up hematology tests to monitor the GOT and GPT of the patients.

2.2.2.2 Indicator of end point

1. Complete resection rate of the gastrointestinal superficial tumors.
2. Follow-ups of wound-healing conditions. Evaluate whether the lifting agent causes any local tissue damage.
3. The incidence of complication is lower than 5% within one month.

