2.2.5.2 Sample size

Period: from the time when IRB approved this trial to December, 2018
 12 patients will be recruited.

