2.2.10 Statistical analysis

2.2.10.1 Hypotheses

This trial is designed to be a single-armed and non-contrast experiment. We aim to evaluate the safety of EnodGel in the clinical use.

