2.2.10.2 Sample size

The purpose of the study is not to compare this new treatment with traditional ones, and thus there is no statistical test to calculate the appropriate number of samples as in the case of general clinical trials. Instead, a small number of samples have been evaluated to test the safety, which is like what researchers do in Phase I Study. Therefore, we recruited 12 patients in total.

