2.2.10.3 Methods for statistical analyses

Descriptive statistics are used to analyze the data in this study.

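### With 12 patients, endpoint 3 (complication incidence below 5%) cannot be supported as a statement about the true rate: even 0/12 leaves rates up to 26.5% unexcluded

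*Combined protocol and SAP*

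**What the plan says.** Section 2.2.2.2 lists three endpoints. The first is a complete resection rate and the second is wound healing at follow-up; neither has a number attached. The third is worded as an assertion with a limit: "The incidence of complication is lower than 5% within one month".

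Section 2.2.10.1 describes the design: "This trial is designed to be a single-armed and non-contrast experiment". The sample size is 12 in section 2.2.2.1, in section 2.2.5.2 ("12 patients will be recruited") and in section 2.2.10.2 ("Therefore, we recruited 12 patients in total"). Section 2.2.10.2 explains that "there is no statistical test to calculate the appropriate number of samples" and likens the study to Phase I work. The whole of section 2.2.10.3 is one sentence: "Descriptive statistics are used to analyze the data in this study".

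Nowhere do the documents say whether the 5% refers to the observed proportion or the underlying rate, whether it is counted per patient or per lesion, what confidence level applies, or what follows if the line is met or missed.

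**The concern.** Safety is part of the primary goal in section 2.2.1 and is the stated aim in section 2.2.10.1. Endpoint 3 is the only endpoint with a numeric threshold, so it is the one most likely to be reported as met or not met. With no interval beside it, a result of 0/12 could be written up as an incidence below 5%, and a reader would take that as a property of the device. The same data would be compatible with a rate several times higher. In the other direction, a single event would put the study over its own line even if the true rate were well under 5%.

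**Working it through.** There is no calculation in the plan to reproduce: it gives no assumed rate, confidence level or power behind the 12. The check therefore asks what 12 patients can say about 5%.

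**Inputs from the documents:** n = 12 (2.2.2.1, 2.2.5.2, 2.2.10.2); threshold below 5% (2.2.2.2); single arm (2.2.10.1); descriptive analysis (2.2.10.3).

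**Assumptions:** the denominator is patients; the level is 95% unless stated otherwise; all patients share one complication rate and are independent.

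**1. Which results meet the line.** 0/12 = 0%; 1/12 = 8.3%. Only zero events qualifies.

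**2. What 0/12 excludes.** The exact (Clopper-Pearson) upper limit for zero events is 1 − (α/2)^(1/n) two-sided, or 1 − α^(1/n) one-sided.
- Two-sided 95%: 1 − 0.025^(1/12) = 26.5%
- One-sided 95%: 1 − 0.05^(1/12) = 22.1%
- Two-sided 80%: 1 − 0.10^(1/12) = 17.5%

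Other interval methods at 95% give the same message: Wilson 24.2% two-sided and 18.4% one-sided; Jeffreys 18.5% and 14.5%. The lowest of these is still nearly three times 5%.

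The highest one-sided confidence that the rate is below 5% after 0/12 is 1 − 0.95^12 = 46.0%. For comparison, 1/12 has an exact two-sided 95% interval of 0.2% to 38.5%.

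**3. How often the line is met or missed.** P(0/12) = (1 − p)^12.

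| True rate p | Line met (0/12) | Line missed (at least one event) |
|---|---|---|
| 2% | 78.5% | 21.5% |
| 4% | 61.3% | 38.7% |
| 5% | 54.0% | 46.0% |
| 10% | 28.2% | 71.8% |
| 15% | 14.2% | 85.8% |

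**4. Size at which zero events would suffice.** The exact limit drops below 5% when 0.95^n falls below the tail probability.
- Two-sided 95%: ln(0.025)/ln(0.95) = 71.9, so n = 72 (limit 4.99%)
- One-sided 95%: ln(0.05)/ln(0.95) = 58.4, so n = 59 (limit 4.95%)

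**5. Counting lesions instead of patients.** 1/20 = 5.0% is not below the line; 1/21 = 4.8% is, but its exact two-sided 95% upper limit is 23.8%, treating lesions as independent. By step 4, even with zero events, 59 to 72 lesions would be needed, an average of 59/12 = 4.9 to 72/12 = 6.0 per patient. The documents do not give the number of lesions per patient.

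**The case against.** The strongest reply is that the plan never claims to show a true rate below 5%. It states no hypothesis, says openly that the sample size was not derived from a test, and promises only descriptive statistics. Read that way, endpoint 3 is a benchmark for the observed proportion, and since no success rule or consequence hangs on it, the probabilities of meeting or missing it describe a decision the plan does not make. Section 2.2.10.2 also works as a general caveat about the small number.

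Much of this stands. The benchmark reading is reasonable, and 12 patients is not a miscalculation. But the text does not say that this is what the 5% means. Section 2.2.10.2 explains why the number is small; it does not limit what may be concluded from the threshold. Even as a benchmark, the endpoint amounts to requiring no complications at all, which the plan does not disclose.

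Three further points are fair but do not change the conclusion. The plan does not settle which events count as a complication, for example bleeding managed during the procedure, and an exact interval is only as good as that definition. Section 2.1 reports that the product's composition was adjusted during the trials, so a single common rate is an assumption. And the past tense in section 2.2.10.2 may mean recruitment is complete, in which case the interval and the limitation matter most in the report.

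**Conclusion.** The concern holds. As a statement about the true rate, endpoint 3 is out of reach with 12 patients: the best possible result, 0/12, leaves rates up to 26.5% unexcluded, about five times the threshold. This rests on a per-patient denominator and a 95% level, neither of which the plan states. The conclusion does not depend on the interval method or on sidedness, and relaxing the level to 80% does not rescue it. The trial itself remains valid as a small descriptive study; what is at risk is an overstated safety conclusion. It should be fixed, and the fix is cheap.

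**What to change.** Keep the sample size at 12 and make three changes.

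1. In 2.2.2.2 and 2.2.10.3, report endpoint 3 as the number and percentage of treated patients with at least one complication within one month, with an exact (Clopper-Pearson) two-sided 95% confidence interval. State which events count as complications.
2. Beside the sample size in 2.2.5.2 and 2.2.10.2, add: *With 12 patients, 0/12 does not exclude true rates up to about 26% (exact two-sided 95%); no claim that the true rate is below 5% will be made.*
3. Keep the 5% figure disclosed as the original descriptive benchmark, noting that only 0/12 meets it. Section 1.2 indicates that recruitment had begun ("Afterwards, we started to recruit patients with all the procedures"), so the figure should be removed only by a dated, explained amendment that says how many patients had been treated and whether complications were already known. If recruitment has finished, carry the same interval and limitation sentence into the report.

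The cost is one amendment, with no extra patients or data. The safety statement becomes less favourable, because 0/12 would appear with its upper limit of 26.5%.

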2.2.3 Ethical considerations

Patients' willingness to participate in clinical trials is respected. They have the freedom to decide whether they want to join the trials or not. They are also entitled to withdraw the clinical trial agreement at any time during the trial with no specific reasons. In addition, physicians won't be unpleasant and biased against the patients. Moreover, the project investigator and sponsors also have the right to terminate the clinical trials.

2.2.4 Data quality assurance

Physicians will try their best to avoid anti-information drugs such as NSAID, which will mislead the interpretation of treatment effects on those who join this clinical trial during observation period.

2.2.5 Patient Population

2.2.5.1 Inclusion/exclusion criteria

The inclusion criteria:

- A. patients over 20 years old
- B. patients who are diagnosed with superficial tumors or polyps via endoscopy
- C. patients with tumor/polyp size over 10mm
- D. patients who never undergo endoscopic therapy before
- E. patients with the polyps of no deep submucosal invasion or metastasis

The exclusion criteria:

- A. patients with other advanced malignant neoplasm
- B. patients with low white blood cell count ($WBC < 2,000 \mu L$), or patients with low platelet count (platelet count $< 50,000 / \mu L$) or abnormal blood coagulation
- C. patients who are currently using anticoagulant and can't stop using the drug

- D. patients whose major organ dysfunction and thus being considered inappropriate to participate the trial
- E. patients who are diagnosed with deep submucosal invasion or metastasis
- F. patients who fail to do follow-up endoscopy evaluations
- G. patients who are allergic to the compositions of our product (sodium alginate or calcium lactate)
- H. patients who don't sign the consent form of participation of this trial

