2.2.6 Clinical management and settings of clinical treatments

After the preparation and patient evaluation for a safe endoscopy, endoscopists will decide to perform ESD or EMR on the patients in accordance with their health condition. During the surgery, the administered dose of EndoGel can be determined based on the size of lesions and the height of submucosal cushions.

After the therapy, we will monitor the vital signs of the patients in wards or endo rooms. We carry out the medical observation in order to react promptly to any immediate adverse events occurring to the patients, such as delayed bleedings and perforations. We will also conduct long term follow-up hematology tests to monitor the GOT and GPT of the patients. Patients can leave hospital in 7 days if they are well recovered. They should also do follow-up examinations to see if there are any complications or adverse events.

All patients will receive the endoscopic follow-up examinations 4 weeks after the endoscopic surgery to evaluate the wound-healing conditions and to check if there is

local recurrence. Patients should go back to the outpatient clinic to do follow-up examinations after the first week and the sixth week.

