2.2.9 Subsequent observation care

Patients will come back to the outpatient clinic after the first week of surgery to see if there is any side effect. They will also do the follow-up endoscopy within 4 weeks to check the wound-healing conditions and if there is any local recurrence. After the 6th week, patients will return again for their check-up.

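### Exclusion criterion F is worded on an event after treatment and no analysis set is stated, so a treated patient with a complication could drop out of the 5% endpoint

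*Combined protocol and SAP*

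**What the plan says.** Section 2.2.5.1 lists, as exclusion criterion F, "patients who fail to do follow-up endoscopy evaluations". Sections 2.2.6 and 2.2.8 place the follow-up endoscopy at 4 weeks after the procedure, and Section 2.2.9 places it within 4 weeks. That difference is editorial: on either wording the examination follows EndoGel.

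Section 2.2.2.2 gives three endpoints, none with a stated denominator:

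1. "Complete resection rate of the gastrointestinal superficial tumors".
2. Wound healing, with the instruction "Evaluate whether the lifting agent causes any local tissue damage".
3. "The incidence of complication is lower than 5% within one month". This is the only endpoint with a numerical limit.

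Complications are looked for during the procedure and in the ward (Sections 2.2.2.1 and 2.2.6), and also in clinic. Section 2.2.6 says "Patients should go back to the outpatient clinic to do follow-up examinations after the first week and the sixth week", and Section 2.2.9 gives the purpose of the first visit: "Patients will come back to the outpatient clinic after the first week of surgery to see if there is any side effect".

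On withdrawal, Section 2.2.3 says "They are also entitled to withdraw the clinical trial agreement at any time during the trial with no specific reasons". On analysis, Section 2.2.10.3 says only "Descriptive statistics are used to analyze the data in this study". Section 2.2.10.1 names safety as the aim, and Section 2.2.10.2 sets 12 patients without a formal calculation.

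**The concern.** An eligibility rule should be decidable before treatment. Read literally, F is not: whether a patient fails to attend the endoscopy is known only weeks after EndoGel has been injected. Patients may withdraw at any time, so a treated patient can miss the examination, and the plan does not say how that patient is then counted.

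The complication endpoint does not need the endoscopy. A perforation or bleed may be known from the procedure, the ward or the week-1 visit. If F were then used to remove the patient for missing the endoscopy, a known safety event would leave both the numerator and the denominator. Safety is the stated aim and this endpoint carries the only numerical limit, so the rule on who is counted should be fixed before results are reported.

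**Working it through.** **Plan's own figures.** The 12 patients and the 5% limit are stated without a derivation, so there is nothing to reproduce. The check is what leaving a patient out does to endpoint 3.

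**Inputs.** N = 12 (Sections 2.2.5.2 and 2.2.10.2); limit below 5% within one month (Section 2.2.2.2); criterion F (Section 2.2.5.1).

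**Step 1: how many events the limit allows.** One event in n patients gives 1/n. Since 1/20 = 5.0%, which is not below 5%, one event misses the limit for every n up to 20. With 12 patients or fewer, endpoint 3 is met only with zero complications.

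**Step 2: effect of leaving one patient out.**

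| Situation | All treated counted | One patient left out |
|---|---|---|
| The only patient with a complication is left out | 1/12 = 8.3%, not met | 0/11 = 0%, met |
| One complication; a patient without one is left out | 1/12 = 8.3%, not met | 1/11 = 9.1%, not met |
| No complications; anyone is left out | 0/12 = 0%, met | 0/11 = 0%, met |

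The exact (Clopper-Pearson) 95% interval is 0.2% to 38.5% for 1/12 and 0% to 28.5% for 0/11. The two results are close as evidence, although they fall on opposite sides of the limit.

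**Step 3: direction.** A result of met means zero events, and removing patients cannot create one. Leaving patients out can therefore change the verdict only from not met to met.

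**Step 4: illustration under assumptions.** Suppose that F is applied after treatment and removes patients from endpoint 3, that k of the 12 patients miss the endoscopy, and that missing it is unrelated to complications. With c complications in total, the chance that all of them fall among the k is C(12 − c, k − c) / C(12, k).

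| | k = 1 | k = 2 | k = 3 |
|---|---|---|---|
| c = 1 | 1/12 = 8.3% | 2/12 = 16.7% | 3/12 = 25% |
| c = 2 | 0% | 1/66 = 1.5% | 10/220 = 4.5% |

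The documents support no value for k or c. These figures show how the route would work and are not estimates of how likely it is.

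**Step 5: whether the text closes the route.** Sections 2.2.10.1 to 2.2.10.3 give a single-arm design, 12 patients and descriptive statistics. The document does not define an analysis or safety set, and does not say how excluded or withdrawn patients are counted or whether they are replaced.

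**The case against.** The strongest reply is that F is a screening rule in loose English. It sits in a list of eight exclusion criteria, and the other seven describe the patient at or before entry. Tense is unreliable in the same section: inclusion criterion D uses the present tense where it plainly means past treatment. Section 2.2.6 also expects every patient to have the follow-up endoscopy. On this reading F means patients who cannot or will not return, and it has no bearing on the analysis.

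That reading is plausible and may be the intended one. It does not settle the matter. The document uses follow-up endoscopy only for the examination after EndoGel, and criterion D requires patients with no earlier endoscopic therapy. Even if F is a screening rule, the missing statement on who is counted remains.

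Three further objections stand in part:

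- Nothing in the plan links F to the analysis. A reader might infer that the plan orders patients with complications to be removed; no section says so.
- A reader might infer that patients with complications are more likely to miss the endoscopy. The documents give no evidence of that, and the point does not need it.
- The reversal is easy because a 5% limit with 12 patients allows no event. That is a separate weakness, but it is also why the denominator matters here.

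It is also true that the trial is descriptive, that no decision is tied to the 5% limit, and that a reported 0/11 against 12 recruited would show that someone is missing. These points limit the consequence; they do not supply the counting rule.

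**Conclusion.** The point holds as an open route to bias, not as a bias that has been shown. Two facts are certain from the text: F is worded on an event after treatment, and no section says that all treated patients are counted. How F would be applied is not certain.

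If it were applied as written to the only patient with a complication, endpoint 3 would go from 1/12 = 8.3% (not met) to 0/11 = 0% (met), and no removal could move it the other way. That size rests on N = 12, on exactly one complication, and on F being used to take patients out of endpoint 3. A reader might take the 8.3%, 16.7% and 25% above as the chance that the endpoint is biased. They are not, because they depend on every assumption listed in that step.

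The sponsor should make the change: the wording is a stated rule, nothing limits its effect, and the repair is cheap.

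**What to change.** 1. **Reword criterion F** as: *patients who, at enrolment, are unable or unwilling to return for the follow-up endoscopy*. This is moot if enrolment is closed, as the past tense in Section 2.2.10.2 suggests. Items 2 and 3 can still be applied at reporting.

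2. **Add a counting rule to Section 2.2.10.3.** Every patient given EndoGel is counted in the complete-resection and complication endpoints, whether or not the follow-up endoscopy is done. Complications are taken from the procedure, hospital records, the week-1 visit, the 4-week endoscopy when done, and the week-6 visit. For endpoint 3, only events with onset within one month count, because the week-6 visit falls outside that window.

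3. **Make incomplete follow-up visible.** Report beside the complication rate the number of patients not followed for the full month, and do not describe them as complication-free. Report wound healing and local tissue damage among patients assessed by endoscopy, with the number not assessed. For example, 1 patient with damage and 2 not assessed is reported as 1 of 10 assessed (10%), 2 not assessed, and not as 1/12 = 8.3%.

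The cost is text only, with no extra visit, procedure or patient. The price is that gaps in follow-up will show in the report.
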